5. AMENDMENTS AND UPDATES

None

6. MILESTONES

Milestones	Planned Date
Registration in the HMA-EMA Catalogues of RWD Studies	03 December 20243 rd , 2024 EUPAS1000000406
Expected date of approval by the central IEC	01 May – 31 May 2025
Expected date of opening of the first site	01 June 2025
Start of data collection	01 June 2025
End of recruitment	30 November 2026
End of data collection	30 November 2027
Interim Analysis after 18m FUP of first 50 patients recruited	30 April 2027
Final study report	31 May 2028

7. RATIONALE AND BACKGROUND

Genomic rearrangements involving ALK have been identified in distinct solid tumors including anaplastic large cell lymphoma (ALCL), diffuse large B cell lymphoma, inflammatory myofibroblastic tumor (IMT), glioma, NSCLC, colorectal, breast, ovarian, and esophageal cancer. ALK rearrangements are found in 3-5% of NSCLC, mainly in lung adenocarcinomas¹.

The resulting ALK fusion proteins retain the entire kinase domain of ALK at the C-terminus, and the N-terminus consists of an entirely different protein. These fusion proteins are validated therapeutic targets. Several large international trials have now validated that patients with ALK positive (ALK+) lung cancer benefit from treatment with ALK TKIs, that became the first-line treatment in patients with advanced NSCLC.

Lorlatinib, a third-generation ALK inhibitor, has shown great potential as a powerful and promising treatment option for managing ALK-rearranged NSCLC. Its unique structure and mechanism of action provide several benefits, including strong inhibition of ALK and other related kinases, as well as the ability to cross the blood-brain barrier, targeting a common site of metastasis in NSCLC.

The CROWN trial 5 was a randomized phase III trial that enrolled a total of 296 patients who were randomly assigned to receive either Iorlatinib or crizotinib as first-line therapy for ALK-positive NSCLC⁷.

At a median of follow up of 60.2 months⁴ (95% CI, 57.4 to 61.6) in the lorlatinib group and 55.1 months (95% CI, 36.8 to 62.5) in the crizotinib group. The HR for PFS or death with lorlatinib versus crizotinib was 0.19 (95% CI, 0.13 to 0.27). Median PFS was NR (95% CI, 64.3 to NR) with lorlatinib and 9.1 months (95% CI, 7.4 to 10.9) with crizotinib. The 4- and 5-year PFS was 63% and 60% (95% CI, 51 to 68) with lorlatinib, respectively, and 10% and 8% (95% CI, 3 to 14) with crizotinib. Among patients with baseline brain metastases (measurable and/or non-measurable; n = 35 in the lorlatinib group and n = 38 in the crizotinib group), the HR for PFS or death with lorlatinib versus crizotinib was 0.08 (95% CI, 0.04 to 0.19); median PFS was NR (95% CI, 32.9 to NR) with lorlatinib and 6.0 months (95% CI, 3.7 to 7.6) with crizotinib. Five-year PFS was 53% (95% CI, 35 to 68) with lorlatinib and not evaluable with crizotinib as all patients had progression or death or were censored within 2 years. Among patients without baseline brain metastases, the HR for PFS or death with lorlatinib versus crizotinib was 0.24 (95% CI 0.16 to 0.36); median PFS was NR (95% CI, 64.3 to NR) with lorlatinib and 10.8 months (95% CI, 9.0 to 12.8) with crizotinib. Five-year PFS was 63% (95% CI, 52 to 71) with lorlatinib and 10% (95% CI, 5 to 18) with crizotinib.

Regarding the safety profile of the drug, the median treatment duration was 57.0 months (IQR, 13.9-63.3) with lorlatinib and 9.6 months (IQR, 4.7-17.1) with crizotinib. Overall, 49 of 149 patients (33%) treated with lorlatinib and 36 of 142 (25%) treated with crizotinib had at least one dose reduction. The median relative dose intensity was 99% (IQR, 80-100) with lorlatinib and 99% (IQR, 91-100) with crizotinib. All-causality any-grade AEs occurred in all patients in the lorlatinib group and in 140 of 142 patients (99%) in the crizotinib group; grade 3/4 AEs occurred in 77% and 57% of patients, respectively. A higher rate of grade 3/4 AEs from any cause in the lorlatinib group compared to the crizotinib group was mostly due to hypertriglyceridemia (25% v 0%), hypercholesterolemia (21% v 0%), weight gain (23% v 2%), and hypertension (12% v 1) with lorlatinib, 23% of patients had dose reduction, 62% had temporary treatment interruption, and 11% had permanent discontinuation because of AEs from any cause. Treatment-related AEs caused

permanent treatment interruption in eight patients (5%), which happened in the first 26 months. With crizotinib, 15% of patients had dose reduction, 48% had temporary treatment interruption, and 11% had permanent discontinuation because of AEs from any cause.

Solomon et al reported lorlatinib is associated with neurologic toxicity (mood/speech and cognitive areas), accounting for 35% of patients in the CROWN trial (3yr follow up of the pivotal trial⁸), being in most patients grade 1. CNS AEs did not have a negative impact on patient-reported quality of life. Most CNS AEs resolved (33% without intervention and 17% with lorlatinib dose modification), while 38% were unresolved; most required no intervention. Lorlatinib dose modification did not influence PFS. Few observational studies have reported the frequency of CNS toxicity on patients with ALK+ NSCLC receiving lorlatinib, however no information is available regarding patients from South Europe. The study will be relevant to learn more about the frequency in our population and about the clinical management in real clinical practice.

Lorlatinib also had a manageable safety profile, with hyperlipidemia, weight gain, and hypertension being the most common G3/4 adverse events and some others with lower frequency as the alterations at the CNS level (mood/speech and cognitive) that generate some uncertainties regarding an adequate management. Occurrence of adverse events with lorlatinib in Spain (2nd and later lines approval in February 2021) is known in later lines of treatment and it seems that several factors involved in that previously treated population (use of radiotherapy, presence/absence of baseline intracranial metastasis, use of concomitant drugs, personal clinical history of psychiatric/mood diseases, etc.) are associated to certain types of AEs, i.e. the CNS adverse events⁶, but the occurrence of those AEs are not well-known with the use of the drug in the first line of treatment (local approval February 2023) and that is one of the reasons why this data gap with lorlatinib should be covered.

On the other hand, real-world evidence is needed to confirm these results in wider patient populations that are seen in regular clinical practice. For example, ethnicity may be an important factor for how well lorlatinib works. With nearly 50% of the patients in the CROWN trial being Asian, PFS HR was 0.47 (95% CI 0.27-0.82) compared to 0.19 (95% CI 0.11-0.32) in non-Asian origin. In CROWN trial, a highly selected group of patients with ALK-positive NSCLC, 20% of patients had disease progression in the first 12 months of treatment. Also, there was no difference in the rate of progression in the first 4 months of treatment with lorlatinib compared to crizotinib, affecting about 12% of the patients. This high risk of disease progression in the first few months of treatment highlights the need for personalized or combinational approach to prevent early disease progression. Real-world data can offer information on the effectiveness, tolerability, and long-term outcomes of lorlatinib as a first-line therapy, adding to the evidence from controlled clinical trials and may help to identify prognostic and predictive factors not fully captured in clinical trials.

In the CROWN trial, molecular profiling tests were analyzed on plasma cfDNA and tumor tissue samples to examine different genomic changes and their relation to treatment outcomes in patients with ALK-positive NSCLC treated with lorlatinib or crizotinib.

Baseline plasma samples were available from 134 patients in the lorlatinib group and 129 in the crizotinib group2. EML4:ALK variant 1 was found in 15% of patients in the lorlatinib group and 20% in the crizotinib group; EML4:ALK variant 3a/b was found in 13% and 18% of patients, respectively. The median PFS was 64.3 months (95% CI, 26.0 to NR) in patients

with EML4:ALK variant 1 and 60.0 months (95% CI, 33.3 to NR) in those with EML4:ALK variant 3a/b in the lorlatinib group; in the crizotinib group, the median PFS was 7.4 months (95% CI, 5.5 to 9.0) and 5.6 months (95% CI, 5.3 to 7.6), respectively. With lorlatinib (n = 97), the median PFS was 51.6 months (95% CI, 16.4 to NR) in the TP53 mutation—positive subgroup and NR (95% CI, 60.0 to NR) in the TP53 mutation—negative subgroup; with crizotinib (n = 100), the median PFS was 5.7 months (5.4 to 7.2) and 9.1 months (7.6 to 11.1), respectively.

Liquid biopsy results can also give information on ctDNA tumor fraction which are the levels of ctDNA released into the blood (a sign of tumor burden or more aggressive biology). Molecular classification of ALK-positive NSCLC may help make treatment decisions, such as combination strategies, when poor prognosis markers are included at diagnosis.

This protocol outlines the methods for a real-world study that assesses how lorlatinib is used as a first-line treatment in patients with ALK-rearranged NSCLC, focusing on its safety and management. By collecting and analyzing data from different sites in Spain, this study aims to show the real-world clinical outcomes, treatment patterns, and safety of lorlatinib, which will help clinicians make better decisions and improve patient care for ALK-positive NSCLC.

This noninterventional study is designated as a PASS and is conducted voluntarily by Pfizer.

The medical literature contains analogous examples of post-authorization safety studies that offer valuable information²⁰⁻²² required by physicians and, in our case, considering that lorlatinib has become the first TKI and biomarker targeted therapy providing the longest efficacy (mPFS not reach after 60.2 months of follow-up in its pivotal trial) reported for all the solid tumors to date⁴.

8. RESEARCH QUESTION AND OBJECTIVES

Research question

 What is the spectrum of adverse events and mitigation strategies associated with lorlatinib as a first line treatment in an ALK+ NSCLC real-world Spanish population?

Primary Objective

• To describe all the spectrum of the adverse events (AEs) of Lorlatinib (CTCAE v6.0) and its mitigation strategies, with special interest in CNS AEs

Secondary Objectives

- To identify factors that are predictive of AEs, with special interest in CNS AEs
- To evaluate the effectiveness of 1L lorlatinib in real-world practice
 - 1. rwPFS rate at 12 and 18 months in the ITT population with and without brain metastasis at baseline.
 - 2. rwDuration of Response (DoR)

- 3. rwDuration of Treatment (DoT)
- 4. rwTime to next therapy/treatment (TTNT)
- 5. rwSystemic and intracranial Objective Response rate (ORR) using Response Evaluation Criteria in Solid Tumors (RECIST v1.1.) criteria
- 6. rwTime to intracranial progression rate at 12 and 18 months with and without brain metastasis at baseline
- 7. rwCumulative incidence of brain metastases (BM) in ITT population at 12 and 18 months (with and without baseline BM)
- 8. rwOverall survival (OS) rate at 12 and 18m
- To evaluate the impact of lorlatinib on patients' quality of life
- To describe ALK testing methods used

Exploratory Objectives (up to 30 patients)

• To identify neuroimaging markers (MRI) that are predictive of the occurrence of CNS AEs

9. RESEARCH METHODS

9.1. Study Design

This is an observational, non-interventional, prospective, multicenter and nationwide study with the category of PASS (Post Authorization Safety Study), which seeks to answer the research question: what is the spectrum of adverse events and mitigation strategies associated with lorlatinib in a real-world Spanish population? For this purpose, an observational, non-interventional and prospective study design is ideal to faithfully reflect what occurs in the routine clinical practice.

It is important to note that our study population exhibits a low incidence of NSCLC patients, approximately 3-4%. Consequently, the current study is descriptive in nature, as it lacks the statistical robustness (relatively small sample, but almost similar to the total of patients included in the pivotal trial) necessary to establish a significant association between a specific adverse event and the drug.

The primary objective will be to describe all the spectrum of the AEs of Iorlatinib (CTCAE v6.0) and its mitigation strategies with special interest in CNS AEs.

Primary Objective	Corresponding Endpoint			
To describe all the spectrum of the adverse events (AEs) of Lorlatinib (CTCAE v6.0) and its mitigation strategies, with special interest in CNS AEs	Occurrence (number of adverse events) and severity of AEs, with severity determined according to NCI CTCAE v6.0 criteria. Frequency and period of dose reductions as well as concurrent medications used to control AEs will be collected			
Secondary Objectives	Corresponding Endpoints			
To identify factors that are predictive of AEs, with special interest in CNS AEs	To evaluate the relationship of multiple demographic and clinical factors with the incidence of AEs, with special interest in CNS adverse events			
To evaluate the effectiveness of 1L lorlatinib in real-world practice	• Effectiveness will be assessed:			
rwPFS rate at 12 and 18 months in the ITT population with and without brain metastasis at baseline	1. To determine real-world progression-free survival (rwPFS) defined as the time from enrollment to the first occurrence of disease progression (intracranial or systemic) or death from any cause, whichever occurs first, as determined by the investigator using RECIST v1.1. criteria, at 12 and 18 months, in the ITT population with and without brain metastasis at baseline			
2. rwDuration of Response (DoR)	2. To determine real world duration of response (DOR), as the time from the first occurrence of a documented objective response to disease progression or death from any cause, whichever occurs first, as determined by the investigator according to RECIST v1.1. criteria (or Time from first documentation of CR or PR (whichever occurs first) after index until death or PD)			
3. rwDuration of Treatment (DoT)	3. To determine duration of treatment (DoT) as the time from lorlatinib's first dose to last dose for any cause. (Time to treatment discontinuation or Time from first dose to last dose of a treatment)			

4.	rwTime to next therapy/treatment (TTNT)	4.	To determine Time to next therapy/treatment (TTNT) as the Time from end of lorlatinib treatment to institution of next therapy	
5.	rwSystemic and intracranial Objective Response rate (ORR) using RECIST v1.1. criteria.	5.	To determine the systemic and real-world intracranial objective response rate (ORR) as determined by the investigator using RECIST v1.1. criteria	
6.	rwTime to intracranial progression rate at 12 and 18 months with and without brain metastasis at baseline	6.	Real world Time to intracranial progression rate at 12 and 18 months with and without brain metastasis at baseline	
7.	rwCumulative incidence of brain metastases (BM) in ITT population at 12 and 18 months (with and without baseline BM)	7.	Real world Cumulative incidence of brain metastases (BM) in ITT population at 12 and 18 months (with and without baseline BM)	
8.	rwOverall survival (OS) rate at 12 and 18m	8.	To determine the real-world overall survival (OS) rate at 12 and 18 months. OS is defined as the time from enrollment to death from any cause	
To evaluate the impact of lorlatinib on patients' quality of life.		of Pl Lo ar	hange from baseline in health-related quality f life (HRQoL), using the EORTC C30, RO_CTCAE (for CNS AEs) and submodules C13 at baseline, C1D15, C2D1, C3D1, C6D1 and every 3 months until the 1st year and then very 6 months	
To describe ALK testing methods used		Describe the different methods used to testing ALK mutations		
Exploratory Objectives (up to 30 patients)			Corresponding Endpoints	
To identify neuroimaging markers (MRI) that are predictive of the occurrence of CNS AEs		Fazekas scale, morphometric and radiomic analysis of baseline magnetic resonance images (MRIs) to identify imaging markers associated with the development of CNS AEs		

All assessments described in this protocol are performed as part of normal clinical practice or standard practice guidelines for the patient population and healthcare provider specialty in the countries where this noninterventional study is being conducted.

Sites: The study will be conducted in approximately 20 Spanish hospitals and the participating physicians will be oncologist specialized in the management of NSCLC.

Study Visits: All assessments described in this protocol are performed as part of normal clinical practice or standard practice guidelines for the patient population and healthcare provider specialty in the local Regions where this non-interventional study is being conducted.

This study will use secondary data from electronic medical records (EMR) and primary data (i.e., newly collected data) collected during routine medical assistance in participating Spanish hospitals. Answers of patients to the questionnaires and items will be collected Informed Consent must be obtained before patients are included in the study and will be collected in paper format.

All assessments described in this protocol are performed as part of normal clinical practice or standard practice guidelines for the patient population and healthcare provider specialty where this noninterventional study is being conducted.

Sample size: In the CROWN trial, the incidence of CNS AEs was 42% and we assumed that the incidence could be higher in the real clinical practice, but it is probably under detected or recorded as most cases are grade 1. We estimated that we need **116 patients** treated with lorlatinib in first-line therapy for ALK+ non-small cell lung cancer with an 80% power to detect an incidence of 55% any grade CNS AEs using a 2-sided test.

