9.2. Setting

The study population includes adult patients aged 18 years or older diagnosed with non-small cell lung cancer who are carriers of the ALK gene rearrangement recruited in an 18-month estimated period from 20 high specialized hospitals at the country level who have started first-line therapy with lorlatinib according to label prescription, with treatment duration of at least 7 days and up to 28 days.

In Spain, molecular diagnosis of ALK rearrangement is routinely performed in patients with non-small cell lung cancer according to the diagnostic guidelines of the Spanish Society of Pathological Anatomy and the Spanish Society of Medical Oncology. Only patients with a confirmed and valid ALK testing will be included in our cohort. Among validated testing methods are the following: FISH fluorescence in situ hybridisation (FISH) Immnunohistochemistry using the D5F3 clon Roche VENTANA (IHC) mainly, PCR polymerase chain reaction (PCR) and the next generation sequencing (NGS)²³.

Given the estimated low incidence rate of 3.4% for this disease among the local population¹⁵, and the difficulty of performing molecular testing in some hospitals at the country level, the

Principal Investigators decided to involve centers specializing in the molecular diagnosis of ALK because otherwise, the lack of expertise in the molecular diagnostics would negatively impact the number of patients that can be enrolled in the study.

Based on data from the CROWN trial, where the incidence of CNS AEs was reported to be 42%, and assuming that the incidence could be higher in real clinical practice but potentially under-detected or recorded as grade 1 cases, they estimated that 116 patients treated with lorlatinib in first-line therapy for ALK+ non-small cell lung cancer are needed. This would provide 80% power to detect an incidence of 55% any grade CNS AEs using a 2-sided test.

Data collection Periods

Patient data will be collected in the following periods:

- **Pre-index period**: since diagnosis to start lorlatinib treatment.
- Index Date: date of start of lorlatinib.
- Post-index period: visits performed under clinical practice since index date and until
 end of study period

Patient data collection will cease at the end of study completion.

Study Visits

The study will be conducted in 5 visits, according to clinical practice:

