9.2.1. Inclusion Criteria

Patients must meet all of the following inclusion criteria to be eligible for inclusion in the study:

- Evidence of histologically or cytologically confirmed diagnosis of locally advanced and/or metastatic NSCLC (Stage IV, AJCC v8.0) harboring an ALK rearrangement identified by an approved diagnostic test. (FISH, IHC, RT PCR, Next generation sequencing, NGS)
- 2. Patients aged ≥18 who have initiated first-line therapy with lorlatinib at least 7 days and up to 28 days prior to enrolment in the study according to routine clinical practice.
- 3. ALK+ patients with intracranial and extracranial disease are allowed.
- 4. Patients should have a minimum of 3 months predetermined data recorded in their medical records.
- 5. Informed consent form personally signed and dated stating that the patient (or their legal representative) has been informed of all relevant aspects of the study.
- 6. ECOG performance status 0-2.
- 7. No previous treatment with an ALK TKI (alectinib, brigatinib, ceritinib, crizotinib. Other systemic treatments if previous relapse in early stages are allowed.

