9.7. Data Analysis

General Considerations

The analysis plan will be fully described in a written and approved statistical analysis plan (SAP). The SAP will describe all statistical analyses, including definition of study outcomes and scoring of the different scales, and will further provide a detailed description of analyses to be performed and describe methods to deal with missing data and censoring. The final SAP will include the tables shell to be used for the final data analyses. Moreover, an interim analysis(es) to characterize dropouts and collecting only critical data elements (ie, variables aligned with the study objectives) to minimize site/participant burden will be conducted.

Descriptive analyses will be carried out to evaluate the objectives of the study. In order to describe the profile of the patients under study, a descriptive statistical analysis of each and every one of the variables included in the notebook will be carried out for this purpose.

Categorical variables are described by their absolute and relative frequency. Continuous variables are described with total n, valid n, n unavailable, means, standard deviation, quartiles, minimum and maximum. Progression-free survival will be measured from treatment initiation to evidence of tumor progression or death. Overall survival will be measured from treatment initiation to death. Patients will be censored at last control, if are lost during the follow-up.

The safety assessment will be based primarily on the frequency and severity of AE. AE will be summarized by presenting the number and percentage of these figures in the total number of patients. The absolute and variable frequencies of each AE with respect to the total number of reported AEs will also be presented. If applicable, the codification of the Medical Dictionary for Regulatory Activities (MedDRA)) will be useful Medication will be coded using WHO Drug Dictionary.

Survival analysis will be performed using Kaplan Meier method. A Cox regression model will be carried out to find independent variables associated with overall survival or time until disease progression.

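### rwPFS and OS start at enrolment in Sections 9.1 and 9.3 but at treatment initiation in Section 9.7, and the two dates lie 7 to 28 days apart in every patient

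*Protocol*

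**What the plan says.** - **Endpoint definitions (Protocol 9.1, repeated in 9.3).** rwPFS is "defined as the time from enrollment to the first occurrence of disease progression (intracranial or systemic) or death from any cause". For survival, "OS is defined as the time from enrollment to death from any cause".
- **Analysis section (Protocol 9.7).** "Progression-free survival will be measured from treatment initiation to evidence of tumor progression or death", and "Overall survival will be measured from treatment initiation to death". Kaplan-Meier and Cox methods are named. Delayed entry is not mentioned.
- **Related dates.** Section 9.2 defines the index date as the "date of start of lorlatinib". Duration of treatment (9.1, 9.3) also runs from first dose.
- **Entry rule (Protocol 9.2.1, criterion 2).** Patients must "have initiated first-line therapy with lorlatinib at least 7 days and up to 28 days prior to enrolment".
- **Records rule (Protocol 9.2.1, criterion 4).** "Patients should have a minimum of 3 months predetermined data recorded in their medical records". The period is not named. The Study Population paragraph of the abstract (Section 4) asks for a minimum of recorded data but gives no three-month figure.

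Nothing in the protocol says which of the two origins prevails.

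**The concern.** Two named endpoints each have two definitions, and criterion 2 ensures that the definitions never agree. An analyst working from the endpoint table and one working from the analysis section would report different 12- and 18-month rates from the same patients. Section 9.7 requires a protocol amendment only for major changes to primary endpoint definitions or their analyses. For these secondary endpoints the choice could therefore be made later without one.

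The choice also affects bias. On the first-dose clock a patient who dies before enrolment can never appear in the data, yet every enrolled patient is credited with the 7 to 28 days already survived. On the enrolment clock those days are not credited, but time zero is an arbitrary on-treatment day that matches neither the index date nor duration of treatment. A progression documented between first dose and enrolment would then fall before time zero, and no rule covers it.

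**Working it through.** The protocol states no rwPFS or OS figure to reproduce. The check is a comparison of the texts followed by a sizing.

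**Inputs**
- Gap w from first dose to enrolment: 7 to 28 days (9.2.1), which is 7/30.44 = 0.23 to 28/30.44 = 0.92 months.
- Section 7 on the pivotal trial: about 12% progressed in the first 4 months and 20% in the first 12. Assumption: these are PFS events counted from first dose, so S(4) = 0.88 and S(12) = 0.80.
- Section 7 also gives 5-year PFS of 60%, used in one variant after month 12.

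**Hazard shapes (assumed), per month**
- A, constant: −ln(0.80)/12 = 0.0186.
- B, falling: −ln(0.88)/4 = 0.0320 to month 4, then −ln(0.80/0.88)/8 = 0.0119, continued after month 12.
- C: as B to month 12, then −ln(0.60/0.80)/48 = 0.0060.

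**Formulas, if everyone enrols on the same day w and any event before w prevents enrolment**
- First-dose clock, delayed entry ignored: S(12)/S(w).
- Enrolment clock: S(12 + w)/S(w).
- Reference value from first dose: 80.0%.

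| Shape | Entry day | S(w) | First-dose clock | Enrolment clock | Difference |
|---|---|---|---|---|---|
| A | 7 | 0.9957 | 80.3% | 80.0% | 0.3 |
| A | 28 | 0.9830 | 81.4% | 80.0% | 1.4 |
| B | 7 | 0.9927 | 80.6% | 80.4% | 0.2 |
| B | 28 | 0.9710 | 82.4% | 81.5% | 0.9 |
| C | 7 | 0.9927 | 80.6% | 80.5% | 0.1 |
| C | 28 | 0.9710 | 82.4% | 81.9% | 0.5 |

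The first-dose clock overstates by 0.3 to 2.4 points and the enrolment clock by 0 to 1.9 points. The two definitions differ from each other by 0.1 to 1.4 points.

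**18 months, first-dose clock**
- A: 71.5% becomes 71.9% to 72.8%.
- B: 74.5% becomes 75.0% to 76.7%.

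**What delayed entry recovers.** A left-truncated curve estimates survival conditional on reaching the earliest entry day. If all patients enrol on one day it equals the ordinary curve. With entry spread evenly over days 7 to 28:
- Shape B: the mean of S(w) is (0.9927 − 0.9710)/(0.0320 × 0.69) ≈ 0.982. The ordinary estimate is 0.80/0.982 = 81.5% and the left-truncated one is 0.80/0.9927 = 80.6%, a change of 0.9 points.
- Shape A: the mean of S(w) is about 0.989, giving 80.9% and 80.3%, a change of about 0.5 points.

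**OS.** The protocol gives no early mortality figure for a first-line population, so no OS size is computed. The inflation factor is 1/S(w). Since survival at w is at least PFS at w, the relative inflation for OS is no larger than for rwPFS.

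**Criterion 4.** If the three months (about 91 days) follow first dose, they cannot have accrued by an enrolment due by day 28. If they precede first dose, they add no event-free time to either clock. If they run from diagnosis to enrolment, the criterion would exclude patients who started lorlatinib less than 91 − 28 = 63 to 91 − 7 = 84 days after diagnosis. Starting the count at diagnosis is an assumption, since medical records may go back further.

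**The case against.** The strongest reply is that this is a drafting slip of little numerical weight. The endpoints are secondary, the study calls itself descriptive, and no formal comparison with the pivotal trial is planned. With 116 patients and a rate of 80%, the 95% half-width is about 1.96 × √(0.80 × 0.20/116) = 7 points, well above any shift computed here. Section 9.7 also leaves outcome definitions and censoring to the SAP. Much of this stands. It limits the weight of the point, and it means that silence on delayed entry is not by itself a protocol error. It does not remove the contradiction, because the protocol itself fixes both origins.

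A second objection is that only death strictly prevents enrolment. No criterion excludes a patient who progressed between first dose and enrolment, and Section 9.2 bars at most those treated for less than 7 days. The first scheduled follow-up visit is at month 3, so little progression may be documented by day 28. This also stands. The sizing lets every early PFS event block entry, so 2.4 points is closer to an upper bound than to an expected value.

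A reader might infer two stronger claims:
- **That both clocks are biased upward.** The documents do not support this. The enrolment clock counts no guaranteed time and shows no bias under a constant hazard. Its bias appears only if the hazard falls after first dose.
- **That criterion 4 guarantees three event-free months.** Under shape B this would give 0.80/0.909 = 88.0% at 12 months, 8 points too high. That reading is incompatible with enrolment by day 28, so the figure should not be used.

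**Conclusion.** The contradiction holds for both rwPFS and OS and follows directly from the text. Guaranteed survival time belongs to the Section 9.7 clock alone, where it is certain for death and only possible for progression. Its cost there is about 0.3 to 2.4 points at 12 months. On the enrolment clock only selection of patients who reached entry remains, worth 0 to about 2 points. These sizes rest on reading the Section 7 progression percentages as PFS events and on the assumed hazard shapes. The consequence is modest and confined to secondary endpoints, but the definitions need correcting before analysis because two sections prescribe different results. Criterion 4 is a separate ambiguity of wording and is not shown to bias either endpoint.

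**What to change.** 1. State one origin for rwPFS and OS in Sections 9.1, 9.3 and 9.7. First lorlatinib dose is preferable because it matches the index date, duration of treatment and the present Section 9.7.
2. With that origin, have patients enter the risk set on their enrolment date (delayed entry) in the Kaplan-Meier and Cox analyses. Report the rates as conditional on reaching the earliest entry day. Delayed entry does not recover the unconditional rate from first dose.
3. State how progression documented between first dose and enrolment is handled.
4. In criterion 4, name the period that the three months covers and reconcile it with the abstract.

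The cost is wording in three sections and one criterion, plus one entry-time argument in the analysis code. Delayed entry should change the 12-month rate by about 1 point or less. Few patients will be at risk in the first weeks of a left-truncated curve, so the numbers at risk should be shown.
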